4.2 SCIENTIFIC RATIONALE FOR STUDY DESIGN

We chose cluster over individual randomization for the benefits of increased efficiency and decreased risk of experimental contamination, while recognizing potential loss in statistical precision from the effects of variance inflation.⁶⁴ However, cluster effects are usually small and can be controlled in analysis. Cluster randomization is also a favorable design strategy for the Type I hybrid effectiveness-implementation approach to test clinical effectiveness while gathering information on implementation.⁶² Hybrid designs are increasingly used to expedite the sequential process, “efficacy to effectiveness to preliminary implementation⁶³ and are recommended when there is strong evidence of the intervention effects and the intervention is low risk for participants.⁶² To maximize data on the implementation process and sustainability, we chose a delayed intervention design⁶⁵ in which clinics are randomized either to implement SPIRIT immediately after randomization (i.e., initial implementation) or to maintain usual care for a comparison condition and then implement the intervention in Year 4 (i.e., delayed implementation). The delayed implementation group will effectively serve as control for effectiveness evaluation. The process outcomes from the initial implementation of SPIRIT will be used to determine if any modifications to SPIRIT are necessary. We anticipate that we will make clinic-specific adaptations to improve implementation in the delayed implementation phase. Clinics in the delayed implementation phase will be evaluated on the process outcomes, which will provide data on the iterated version of SPIRIT without having to conduct another trial. The

delayed implementation is more ethical than not providing SPIRIT at all because its demonstrated efficacy would preclude equipoise.

Virtually no trials are purely pragmatic or explanatory; based on the PRECIS Tool and key characteristics of pragmatic trials,^{66,67} the proposed study is more pragmatic than explanatory in the pragmatic-explanatory continuum because it will include diverse patient populations, multiple heterogeneous settings, few inclusion and exclusion criteria, and the comparison condition is a real-world alternative (i.e., usual care), not a placebo. Further, the study is built around normal dialysis care operations as much as possible with flexible study protocols that minimize intrusion in daily work flow at the dialysis facilities. Of direct relevance to dialysis care, the intervention will be implemented by dialysis care providers, such as nurses and social workers.

For Supplement Aims:

As in our previous studies of SPIRIT, we chose individual randomization because intervention spillover to the control condition is very unlikely. The intervention will be delivered by a trained interventionist, not a care provider, in a private room at the clinic, or virtually due to the COVID-19 pandemic, and thus it is nearly impossible for care providers to obtain the knowledge and skill related to SPIRIT to change their ACP practice. We chose race (white vs non-white) as a stratification factor to ensure equal allocation of race to each condition to control for race as a confounding variable.⁴⁹

The follow-up time point (2-3 days post intervention) is to evaluate the impact of SPIRIT on preparedness outcomes while minimizing the potential influence of the patient's impaired ability to recall what was discussed during the SPIRIT session. We considered measuring the outcomes immediately following the intervention, but this would increase subject burden as SPIRIT sessions tend to last longer with PWDs than those without cognitive impairment. The time point for care decision reviews (6 months post intervention) was chosen to help maximize the number of patients whose conditions progress within the study period so that we can explore the impact of SPIRIT-dementia on care decisions. As in earlier SPIRIT trials and the parent study with ESRD patients and the parallel study with dementia patients, we will use telephone-based data collection to reduce participants' travel burden.

Supplement cohort study:

We posit that reflexive decision-making in response to the pandemic could discount previously expressed preferences for end-of-life care, thereby affecting the stability of those preferences. We postulate that such alterations in decisions may be more prevalent among patients and families who have not had ACP to explore own values and beliefs about end-of-life care (such as dyads in the control group in the parent study), and also among Blacks, a racial group that is thought to embrace more aggressive treatment at the end of life.²⁹ This is especially important now in light of recent findings³⁰ that counties in the U.S. with higher Black populations account for more than half of all COVID-19 cases and almost 60% of deaths even though Blacks represent only 13.4% of the American population. We have an opportunity to address these complicated but urgent questions about end-of-life decision making when people fear a dangerous virus and are alarmed about scarce lifesaving resources, such as ICU beds and ventilators.

4.3 JUSTIFICATION FOR INTERVENTION

The SPIRIT intervention is a one-time advance care planning intervention that has been rigorously tested and has demonstrated its efficacy. The details about the intervention, including the rationale, are described above (2.2 Background).

4.4 END OF STUDY DEFINITION

Because the study uses a delayed intervention design to maximize implementation data collection, the end of the study will be the completion of care provider acceptability, fidelity and cost data collection.

For Supplement Aims:

We will review the patient's medical record to examine care decisions at 6 months or after the patient's death, whichever occurs first. In the case of patient death, we will also assess surrogates' post-bereavement outcomes (anxiety and depression symptoms) at 1 month after the patient's death. Based on previous research,¹³ we anticipate about 50% of the supplement sample will die within 12 months of enrollment.

Supplement cohort study:

Completion of 6 month follow-up (T4) after T3.

5 STUDY POPULATION

5.1 INCLUSION CRITERIA

Patient eligibility criteria:

- a) 18 years or older
- b) on either hemodialysis or peritoneal dialysis
- c) able to understand and speak English.

Surrogate eligibility criteria:

- a) 18 years or older (to serve as a surrogate decision-maker, the individual must be an adult)
- b) being chosen by the patient.

Roughly 76 providers at the 29 clinics, including all medical directors, nurse managers, social workers, and those who are selected to conduct SPIRIT sessions will participate in the implementation evaluation.

For Supplement Aims:

Patient eligibility criteria:

- a) Receiving in-center hemodialysis at Emory or UVA dialysis clinics.
- b) Diagnosed with dementia of any etiology (or those for whom their care providers, either MD or APRN, are suspicious of dementia) with having mild to moderate cognitive impairment based on a Montreal Cognitive Assessment (MoCA) score of 13 or higher,^{54,55} or a Saint Louis University Mental Status (SLUMS) score of 21 or higher (high school education) or 20 or higher (less than high school education)⁵⁶
- c) Able to understand and speak English
- d) A UBACC (decision-making capacity screening test) score ≥ 11 . Because dementia is largely under-diagnosed in the clinical setting for patients with ESRD, to identify additional patients with possible dementia, a trained research assistant will administer the MoCA or SLUMS to patients who are suspected (by dialysis clinicians) of having dementia. MoCA or SLUMS will take about 10 minutes to complete.

Surrogate eligibility criteria:

- a) 18 years or older (to serve as a surrogate decision-maker, the individual must be an adult)
- b) being chosen by the patient.

For supplement cohort study:

Dyads who completed the parent study's baseline (T1) and 2-week follow-up (T2) before March 13, 2020.

5.2 EXCLUSION CRITERIA

Patient exclusion criteria:

- a) lack of an available surrogate,
- b) too ill or cognitively impaired to participate based on clinicians' judgment*,
- c) already enrolled in hospice.

Surrogate exclusion criterion:

- a) Those who cannot complete questionnaires due to physical or cognitive limitations will be excluded.

For Supplement Aims:

Patient exclusion criteria:

- a) lack of an available surrogate,
- b) uncompensated hearing deficits,
- c) already enrolled in hospice.

***Patients who are excluded from the parent study will be considered for the supplement study.**

5.3 LIFESTYLE CONSIDERATIONS

Not applicable

5.4 SCREEN FAILURES

Because patients are approached first at the dialysis center, it is possible that patients provide written consent to participate in the study with the assumption that their surrogates would be willing to participate with them (however, patients cannot complete the baseline without willing surrogates), and then the surrogate actually declines to participate. Because randomization occurs at the clinic level, not the individual level, these cases will be reported under "not eligible" with reason.

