1.2 SCHEMA

1.3 SCHEDULE OF ACTIVITIES (SOA): Randomization occurs at the clinic level

Days offset	Procedure	Note
Patients and surrogates	Patient referrals ^a	Screened and willing patients
	Patient screened (by research staff) ^b	Linked to eligibility checklist
Day -14 to Day -7	Obtaining patient informed consent in person ^b	Scan and upload signed consent pdf
	Obtaining contact information ^b	
	Medical record review: clinical characteristics ^b	To be linked to "pt consent"
	Usual care review 1 ^b	To be linked to "pt consent" & separate Every 6 months
Day 0	Surrogate verbal consent ^b	
	Surrogate verbal consent received ^b	
	Scheduling baseline (T1) appointment	If control, schedule both T1 & T2
	Reminder call for T1	
Day 14 (+/- 7)	Baseline (T1)-patient completion	Link to the measures
	Baseline (T1)-surrogate completion	Link to the measures
	Payment (T1) mailed to patient	With thank-you note
	Payment (T1) mailed to surrogate	With thank-you note
	Scheduling SPIRIT Session I & II and 2-wk F/U ^b	Need to coordinate with the care provider for SPIRIT sessions
	SPIRIT Session I^a	
	SPIRIT Session II reminder call ^b	Two days prior
	SPIRIT Session II^a	
	SPIRIT Interview Guide Checklist ^b	Care provider interventionist completes and the Site Coordinator enters to REDCap
	Reminder call for T2	Central
	2-week follow-up (T2)-patient completion	2 weeks from SPIRIT; including acceptability survey and SPIRIT components
	2-week follow-up (T2)-surrogate completion	2 weeks from SPIRIT; including acceptability survey and SPIRIT components
	Payment (T2) mailed to patient	With thank-you note
	Payment (T2) mailed to surrogate	With thank-you note
	Monthly check-in call 1	1 month from T2
	Monthly check-in call 2	
	Monthly check-in call 3	
	Monthly check-in call 4	
	Monthly check-in call 5	
	Usual care review 2 ^a	May need one more
	Monthly check-in call 6	
	Monthly check-in call 7	
	Monthly check-in call 8	
	Monthly check-in call 9	With note on study completion
	Mailing sympathy card	Upon patient death
	Contacting surrogate & scheduling a 3-month post-death F/U	
	Postcard reminder 2 weeks before the F/U	
	Reminder call for 3-month F/U	
	F/U 3 month post death	
	Payment (F/U 3M) mailed to surrogate	With thank-you note
	Clinic-level contextual data ^b	At the end of each implementation
Care providers	Informed consent ^b	At the end of each implementation
	Acceptability assessment^b	Brief survey and interview
	SPIRIT care provider interview-sustainability^b	

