Recruitment will occur over 24 months beginning at the end of Year 1. We are highly experienced in recruiting seriously ill ESRD patients and their surrogates for research. Consent rates in our previous studies have been consistent at approximately 84% despite the studies' focus on end-of-life, the requirement that both patient and surrogate participate, and long-term follow-up. We expect a similar if not higher consent rate because the study involves a shorter follow-up time and minimal data collection directly from patients and surrogates. Based on our previous studies,¹⁸⁻²⁰ we conservatively anticipate that 427 patients (20%) will be *eligible and willing* to participate. To reach 400 dyads, we expect to enroll 21-22 dyads per cluster on average. These clinics each accept 10-70 new patients each year (total 700 additional patients), and thus our recruitment goal is readily achievable.

To Maximize Participant Retention, strategies found effective in retaining dyads over 12 months (dropouts, 3.8%) in our efficacy trial²⁰ will be used: we will

- a) obtain two backup contacts from each member of the dyad in the event that we cannot reach them by telephone and mail
- b) make confirmation phone calls 2 days prior to each follow-up
- c) make monthly check-in calls
- d) send holiday cards
- e) assign the same data collector whenever possible
- f) compensate each member of the dyad with gift cards (\$15 at baseline, \$15 at 2 weeks for the preparedness outcome assessment; \$20 at 3 months for the post-bereavement outcome assessment). Consistent with a pragmatic trial, participants will not be compensated for participating in the intervention. The Emory Study Coordination Center will be responsible for disbursement.

For Supplement Aims:

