6.3 MEASURES TO MINIMIZE BIAS: RANDOMIZATION AND BLINDING

Clinics covered by the same care provider who will deliver SPIRIT sessions will be combined to one cluster to avoid risk of contamination; this results in clusters (4 in GA, 3 in NC, 8 in NM, 5 in PA and 8 in VA). Because the numbers of available patients substantially vary across the clusters, to minimize group imbalance clusters will be stratified to three sizes: small (patient census ≤ 52), medium (53-105), and large (≥ 106). We will randomize clusters to either SPIRIT or usual care plus delayed SPIRIT, with randomly permuted blocks (sizes of 2 and 4) within cluster size stratum nested in each state, using a pseudo-random-number generator, by the Study Coordination Center.

Before the study starts, the Study Coordination Center will inform the group assignment for each cluster to the site PIs, with a unique ID consisting of abbreviations for state and cluster size stratum. While the heterogeneity in minority race/ethnicity across clusters improves the study's generalizability, stratification or pairing clusters by race/ethnicity is not feasible because some clinics uniquely serve one race with no comparable clinics within state. Group imbalances on race/ethnicity and other potential confounding factors will be examined and adjusted for in the analyses. The cluster randomized design prevents blinding patient-surrogate dyads and dialysis care providers to group allocation. However, research staff assessing effectiveness outcomes will be blind to group assignment.

For Supplement Aims:

[name] (biostatistician/Co-I) will generate a randomization scheme using stratified (by race), permuted block randomization with block size 5, using a random-number generator. Dyads will be randomized with equal allocation (1:1) to SPIRIT or usual care. Due to the nature of the intervention, blinding dyads to their group allocation is impossible, but the research staff assessing outcomes will be blind. Immediately after the completion of the baseline assessment by phone, the data collector will open a sealed envelope to identify group assignment and schedule an intervention session to take place ~ 2 weeks hence for SPIRIT as well as a follow-up data collection session in the next 2-3 days.

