10 SUPPORTING DOCUMENTATION AND OPERATIONAL CONSIDERATIONS

10.1 REGULATORY, ETHICAL, AND STUDY OVERSIGHT CONSIDERATIONS

10.1.1 INFORMED CONSENT PROCESS

10.1.1.1 CONSENT/ASSENT AND OTHER INFORMATIONAL DOCUMENTS PROVIDED TO PARTICIPANTS

Consent forms describing in detail the study intervention, study procedures, and risks are given to the participant and written documentation of informed consent is required prior to starting intervention/administering study intervention. The following consent materials are submitted with this protocol.

- Patient Consent Form-SPIRIT
- Patient Consent Form-Usual Care
- Surrogate Verbal Consent Form –SPIRIT
- Surrogate Verbal Consent Form – Usual Care
- Care Provider Verbal Consent Form
- VERBAL Consent Addendum – Patient
- VERBAL Consent Addendum - Surrogate

For Supplement Aims, the following consent materials will be used:

- Patient Verbal Consent for Screening (cognitive impairment level)
- Patient Consent Form
- Surrogate Verbal Consent Form

Supplement cohort study:

- Verbal Consent Addendum for Cohort – Patient
- Verbal Consent Addendum for Cohort - Surrogate

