10.1.1.2 CONSENT PROCEDURES AND DOCUMENTATION

Participating dialysis centers/clinics will be randomized first (see the study flow diagram). The care team member who has been selected by the clinic as a care provider responsible for SPIRIT delivery at each clinic in both groups (e.g., nurse or social worker) will generate a list of patients each quarter based on the inclusion criteria. This staff member may differ from clinic to clinic depending on who is qualified, comfortable and able to assess each potential participant. The medical director of the dialysis unit (and/or the attending physician as required) approves the list if required by the dialysis center. From this list, one of the care providers will then assess the patient's willingness to meet with a recruiter from the research team. The recruiter (e.g., site coordinator) will then approach willing patients during their scheduled dialysis clinic appointment.

Consent forms have been Institutional Review Board (IRB)-approved and the participant will be asked to read and review the document. In a private room, a verbal explanation will be provided in terms suited to the patient's comprehension of the purposes, procedures, and potential risks of the study and of their rights as research participants. Patient participants will have the opportunity to carefully review the written consent form (including HIPAA authorization form) and ask questions prior to signing. The patient participants should have the opportunity to discuss the study with their family or surrogates or think about it prior to agreeing to participate. The patient participant will sign the informed consent document prior to any procedures being done specifically for the study. Patient participants must be informed that participation is voluntary and that they may withdraw from the study at any time, without prejudice. A copy of the informed consent document will be given to the

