10.1.6 SAFETY OVERSIGHT

Safety oversight will be under the direction of a Data and Safety Monitoring Board (DSMB) composed of 5 individuals with the appropriate expertise, including dialysis care, advance care planning, palliative care, clinical trials, intervention testing, and biostatistics. Members of the DSMB are independent from the study conduct and free of conflict of interest (see signed disclosure forms).

The DSMB will meet bi-annually to evaluate the study progress, including assessment of data quality, timeliness, participant recruitment, rates of eligibility and ineligibility across study clinics and sites/states, accrual and retention, participant risk versus benefit, performance of trial sites, patient deaths, and any adverse events or care providers' concerns that can affect study outcome. Consistent with prior end-of-life communication interventions, including our prior trials, we do not expect that the intervention will alter mortality rates. Nonetheless, this will be one of the measures monitored by the DSMB. The DSMB will compare recruitment rate and sample characteristics to assumptions used for power calculations. The DSMB will monitor the design factor, intra-cluster correlation coefficient, to assess whether the study will have expected power. Formal interim analyses are not planned for several reasons: (a) the SPIRIT efficacy has been established, (b) risks associated with SPIRIT are very minimal, (c) the control condition is usual care, not a placebo, and (d) the proposed study also aims to gather implementation data, including sustainability, that are critical for widespread implementation. Finally, the DSMB will not monitor fidelity/adherence data and make recommendations for ways to improve adherence because of the pragmatic nature of the proposed trial (i.e., seeking real world answers). The DSMB will operate under the rules of an approved charter that will be written and reviewed at the organizational meeting of the DSMB.

See DSMB Charter.

For Supplement Aims:

Although the proposed study involves minimal risk, we will implement a data and safety monitoring plan at multiple levels to ensure the safety of participants and the validity and integrity of the data:

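### Section 5.4 classes a surrogate's refusal after patient consent as ineligibility, although the clinic is already randomised and the arm is known, and no count or comparison by arm is planned

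*Combined protocol and SAP*

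**What the plan says.** - **Section 5.4 (Screen Failures)** describes a patient who has given written consent, "and then the surrogate actually declines to participate". Its rule is: "Because randomization occurs at the clinic level, not the individual level, these cases will be reported under 'not eligible' with reason". It adds that a patient cannot complete the baseline assessment without a willing surrogate.
- **Section 10.1.1.2 (Consent Procedures)** puts clinic randomisation ahead of patient listing and approach. Section 6.3 agrees: "Before the study starts, the Study Coordination Center will inform the group assignment for each cluster to the site PIs". It also states that dyads and dialysis care providers cannot be blinded.
- **Section 10.1.1.1** lists separate patient and surrogate consent forms for each arm, for example "Patient Consent Form-Usual Care".
- **Section 6.1.1** has patient and surrogate attend two SPIRIT sessions together, with Zoom possible for surrogates living or working more than 50 miles from the clinic. Outcome data in both arms are collected by telephone (8.1), and participants are not paid for attending the intervention (5.5).
- **Section 5.2** excludes patients who have no available surrogate.
- **Section 10.1.6** has the DSMB review "rates of eligibility and ineligibility across study clinics and sites/states". Arm is not mentioned.
- **Section 7.2** allows replacement of subjects at initial-SPIRIT clinics who signed consent but did not receive the intervention. It gives no matching rule for usual care.

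**The concern.** Section 5.4 treats clinic-level randomisation as the reason why a declined surrogate is a screening matter. The logic runs the other way. In a cluster trial that recruits after allocation, every consenting patient already belongs to an arm, so anyone lost between patient consent and baseline is lost after allocation. Clinic-level randomisation is the reason to track such losses by arm.

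The two arms also put different requests to the surrogate. If more surrogates decline under SPIRIT, and those who decline differ from those who accept, the enrolled dyads are no longer comparable even though the clusters were randomised. Dyad congruence, surrogate confidence and the composite all use surrogate responses. Patient decisional conflict is self-reported, but it too is observed only when the surrogate agrees.

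What is at stake is the ability to detect this. Once refusals are pooled with ineligibility, the standard tables will not show whether recruitment after allocation differed between the arms.

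**Working it through.** The plan gives no refusal rate and no figure to reproduce, so the main check sets the sections against each other.

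**1. Does the refusal follow allocation?** Yes. Clinics are randomised first (10.1.1.2), sites are told the assignment before the study starts (6.3), and the surrogate is telephoned several days after the patient signs (5.5).

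**2. Is the arm known when the surrogate decides?** Yes. Dyads are unblinded (6.3) and the surrogate consent form is specific to the arm (10.1.1.1).

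**3. Do the eligibility criteria cover the case?** Only in part. The exclusion in 5.2 concerns lack of an available surrogate. Section 5.4 describes a surrogate whom the patient expected to take part and who then declines.

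**4. Is a comparison by arm planned anywhere?** None is stated. The DSMB item is by clinic and site or state (10.1.6). The intent-to-treat statement (9.3) and the baseline comparison (9.4.1) concern participants.

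**5. Is the counting rule unique?** No. SPIRIT sessions are for patient and surrogate together, so a consented SPIRIT patient whose surrogate declines has signed but cannot receive the intervention. That case is ineligible under 5.4 and replaceable under 7.2.

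**6. Do data exist on these patients?** The schedule in section 1.3 ties "Medical record review: clinical characteristics" and the first usual-care review to patient consent and lists both before surrogate consent.

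**Illustration of size (all inputs assumed).** Let there be no treatment effect, and let congruence among all consented patients' dyads be 0.48 in both arms. The value 48% appears in the power table of 9.2. Let accepting dyads exceed declining dyads by a gap g, the same in both arms. With refusal rate r in an arm:

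- observed congruence in that arm = 0.48 + r × g
- spurious difference = (r_SPIRIT − r_control) × g

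The control rate is set at 6%. This is near 1 − 400/427 = 6.3%, the gap in 5.5 between patients expected to be eligible and willing and the target. That gap is not a surrogate refusal rate; it only gives an order of magnitude.

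| Refusal, control | Refusal, SPIRIT | g = 10 points | g = 30 points |
|---|---|---|---|
| 6% | 6% | 0 | 0 |
| 6% | 12% | 0.06 × 0.10 = 0.6 points | 0.06 × 0.30 = 1.8 points |
| 6% | 16% | 0.10 × 0.10 = 1.0 point | 0.10 × 0.30 = 3.0 points |

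As odds ratios, the second row gives (0.492/0.508)/(0.486/0.514) = 1.024 and (0.516/0.484)/(0.498/0.502) = 1.075.

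For scale, the planned effect on congruence is an odds ratio of 2.0. If 48% is the control rate, which the table does not say, SPIRIT would be 2 × 0.48/(1 + 0.48) = 64.9%, a difference of 16.9 points.

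**The case against.** **The cases are not hidden.** This stands. The rule requires the reason to be recorded and clinic determines arm, so a count by arm can be built afterwards. A reader might infer that the rule conceals differential refusal. The text does not support that: the cases are misclassified but recoverable.

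**The label has some basis.** This stands in part. A patient whose chosen surrogate declines can be said to lack an available one under 5.2. But that is not the reason 5.4 gives, and it would not change the timing of the loss.

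**Relabelling changes neither who is enrolled nor the primary analysis set.** Correct. Any selection arises from open recruitment after cluster allocation, whatever the label. The correction gives detection, not removal.

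**Baseline checks already exist.** Sections 6.3 and 9.4.1 compare the arms at baseline and provide for adjustment, and the preparedness measures are taken before SPIRIT. A marked difference in surrogate preparedness could show there. These checks cover enrolled dyads only and do not directly show how many were lost, or who.

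**The DSMB may see arm-level data.** Possible. Section 10.1.6 defers to a charter that is not among the documents, and the study schema is not shown. The available text neither promises nor excludes it.

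**The earlier consent rate.** A reader might infer that this trial's consent rate can no longer be compared with the roughly 84% in 5.5, obtained despite "the requirement that both patient and surrogate participate, and long-term follow-up". The documents define neither this trial's denominator nor how the earlier rate was counted, so that inference is unsupported.

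**Conclusion.** Section 5.4 misclassifies a post-allocation refusal as ineligibility and gives a reason that points the other way. This rests on the documents alone: the order of randomisation and consent, the absence of blinding, the arm-specific forms, and the lack of any stated comparison by arm. It is a reporting and monitoring defect that should be corrected. It does not invalidate the primary analysis.

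It would be tempting to conclude that the primary result is biased in SPIRIT's favour. The documents do not show that refusal differs by arm, that declining dyads would be less congruent, or in which direction any difference would run. A surrogate who declines because of time or travel need not understand the patient's wishes less well. The illustrated 0.6 to 1.8 points depends on assumed rates and an assumed gap. It is zero if refusal and the gap are equal across arms, changes sign if the gap does, and is small against the planned effect unless the imbalance is large.

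**What to change.** 1. Reword 5.4 so that a consented patient whose surrogate declines is reported as non-enrolment by refusal, by arm and cluster, on its own line in the participant flow and separate from ineligibility.
2. Show these counts to the DSMB by arm.
3. Compare these patients with enrolled patients, within each arm, on the medical-record and usual-care items scheduled at patient consent.
4. Reconcile 5.4 with 7.2, so that a consented SPIRIT patient with a declining surrogate has one classification, and state the corresponding rule for usual care.
5. Treat inverse-probability weighting for surrogate enrolment as optional and exploratory. State that it can use record covariates only (such as modality, years on dialysis, comorbidity and advance-directive or DNR status) and cannot correct for surrogate engagement, which is unmeasured in those who decline.

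The cost is a reworded rule in 5.4, a clarifying line in 7.2, and one table by arm. No new data collection is needed if sites complete the record reviews at patient consent as scheduled and keep them when the surrogate declines.
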